## 5.2 SAFETY PARAMETERS AND DEFINITIONS

Safety assessments will consist of monitoring and recording adverse events, including serious adverse events and adverse events of special interest, performing protocol-specified safety laboratory assessments, measuring protocol-specified vital signs, and conducting other protocol-specified tests that are deemed critical to the safety evaluation of the study.

Certain types of events require immediate reporting to the Sponsor, as outlined in [Section 5.4](#)

### **5.2.1 Adverse Events**

According to the ICH guideline for GCP, an adverse event is any untoward medical occurrence in a clinical investigation subject administered a pharmaceutical product, regardless of causal attribution. An adverse event can therefore be any of the following:

- Any unfavorable and unintended sign (including an abnormal laboratory finding), symptom, or disease temporally associated with the use of a medicinal product, whether or not considered related to the medicinal product
- Any new disease or exacerbation of an existing disease (a worsening in the character, frequency, or severity of a known condition), except as described in Section [5.3.5.10](#)
- Recurrence of an intermittent medical condition (e.g., headache) not present at baseline
- Any deterioration in a laboratory value or other clinical test (e.g., X-ray) that is associated with symptoms or leads to a change in study treatment or concomitant treatment or discontinuation from study drug
- Adverse events that are related to a protocol-mandated intervention, including those that occur prior to assignment of study treatment (e.g., screening invasive procedures such as biopsies)

### **5.2.2 Serious Adverse Events (Immediately Reportable to the Sponsor)**

A serious adverse event is any adverse event that meets any of the following criteria:

- Is fatal (i.e., the adverse event actually causes or leads to death)
- Is life threatening (i.e., the adverse event, in the view of the investigator, places the patient at immediate risk of death)
  - This does not include any adverse event that had it occurred in a more severe form or was allowed to continue might have caused death.
- Requires or prolongs inpatient hospitalization (see Section [5.3.5.11](#))
- Results in persistent or significant disability/incapacity (i.e., the adverse event results in substantial disruption of the patient's ability to conduct normal life functions)
- Is a congenital anomaly/birth defect in a neonate/infant born to a mother exposed to study drug
- Is a significant medical event in the investigator's judgment (e.g., may jeopardize the patient or may require medical/surgical intervention to prevent one of the outcomes listed above)

The terms "severe" and "serious" are not synonymous. Severity refers to the intensity of an adverse event (e.g., rated as mild, moderate, or severe, or according to NCI CTCAE; see Section [5.3.3](#)); the event itself may be of relatively minor medical significance (such as severe headache without any further findings).

Severity and seriousness need to be independently assessed for each adverse event recorded on the eCRF.

Serious adverse events are required to be reported by the investigator to the Sponsor immediately (i.e., no more than 24 hours after learning of the event; see Section 5.4.2 for reporting instructions).

### **5.2.3 Adverse Events of Special Interest (Immediately Reportable to the Sponsor)**

Adverse events of special interest are required to be reported by the investigator to the Sponsor immediately (i.e., no more than 24 hours after learning of the event; see Section 5.4.2 for reporting instructions). Adverse events of special interest for this study include the following:

- Cases of potential drug-induced liver injury that include an elevated ALT or AST in combination with either an elevated bilirubin or clinical jaundice, as defined by Hy's law (see Section 5.3.5.7).
- Suspected transmission of an infectious agent by the study drug, as defined below:

Any organism, virus, or infectious particle (e.g., prion protein transmitting transmissible spongiform encephalopathy), pathogenic or non-pathogenic, is considered an infectious agent. A transmission of an infectious agent may be suspected from clinical symptoms or laboratory findings that indicate an infection in a patient exposed to a medicinal product. This term applies only when a contamination of the study drug is suspected.

## **5.3 METHODS AND TIMING FOR CAPTURING AND ASSESSING SAFETY PARAMETERS**

The investigator is responsible for ensuring that all adverse events (see Section 5.2.1 for definition) are recorded on the Adverse Event eCRF and reported to the Sponsor in accordance with instructions provided in this section and in Section 5.4, Section 5.5 and Section 5.6.

For each adverse event recorded on the Adverse Event eCRF, the investigator will make an assessment of seriousness (see Section 5.2.2 for seriousness criteria), severity (see Section 5.3.3), and causality (see Section 5.3.4).

### **5.3.1 Adverse Event Reporting Period**

Investigators will seek information on adverse events at each patient contact. All adverse events, whether reported by the patient or noted by study personnel, will be recorded in the patient's medical record and on the Adverse Event eCRF.

**After informed consent has been obtained but prior to initiation of study drug**, only serious adverse events caused by a protocol-mandated intervention (e.g., invasive

procedures such as biopsies, discontinuation of medications) should be reported (see Section 5.4.2 for instructions for reporting serious adverse events).

**After initiation of study drug**, all adverse events will be reported until 96 weeks after the end of the Treatment Period, but may be extended in patients whose B-cells take longer to replete.

Related SAEs must be collected and reported regardless of the time elapsed from the last study drug administration, even if the study has been closed.

Instructions for reporting adverse events that occur after the adverse event reporting period are provided in Section 5.6.

### **5.3.2 Eliciting Adverse Event Information**

A consistent methodology of non-directive questioning should be adopted for eliciting adverse event information at all patient evaluation time points. Examples of non-directive questions include the following:

"How have you felt since your last clinic visit?"

"Have you had any new or changed health problems since you were last here?"

### **5.3.3 Assessment of Severity of Adverse Events**

The adverse event severity grading scale for the NCI CTCAE (v4.0) will be used for assessing adverse event severity. Table 3 will be used for assessing severity for infusion related reactions and adverse events that are not specifically listed in the NCI CTCAE.

**Table 3 Adverse Event Severity Grading Scale for IRRs and Other Events Not Specifically Listed in NCI CTCAE**

Grade	Severity
1	Mild; asymptomatic or mild symptoms; clinical or diagnostic observations only; or intervention not indicated
2	Moderate; minimal, local, or non-invasive intervention indicated; or limiting age-appropriate instrumental activities of daily living a
3	Severe or medically significant, but not immediately life-threatening; hospitalization or prolongation of hospitalization indicated; disabling; or limiting self-care activities of daily living b,c
4	Life-threatening consequences or urgent intervention indicated d
5	Death related to adverse event d

NCI CTCAE = National Cancer Institute Common Terminology Criteria for Adverse Events.

Note: Based on the most recent version of NCI CTCAE (v4.0), which can be found at: [http://ctep.cancer.gov/protocolDevelopment/electronic\\_applications/ctc.htm](http://ctep.cancer.gov/protocolDevelopment/electronic_applications/ctc.htm)

- a Instrumental activities of daily living refer to preparing meals, shopping for groceries or clothes, using the telephone, managing money, etc.
- b Examples of self-care activities of daily living include bathing, dressing and undressing, feeding oneself, using the toilet, and taking medications, as performed by patients who are not bedridden.
- c If an event is assessed as a "significant medical event," it must be reported as a serious adverse event (see Section 5.4.2 for reporting instructions), per the definition of serious adverse event in Section 5.2.2.
- d Grade 4 and 5 events must be reported as serious adverse events (see Section 5.4.2 for reporting instructions), per the definition of serious adverse event in Section 5.2.2

### **5.3.4 Assessment of Causality of Adverse Events**

Investigators should use their knowledge of the patient, the circumstances surrounding the event, and an evaluation of any potential alternative causes to determine whether an adverse event is considered to be related to the study drug, indicating "yes" or "no" accordingly. The following guidance should be taken into consideration (see also [Table 4](#)):

- Temporal relationship of event onset to the initiation of study drug
- Course of the event, considering especially the effects of dose reduction, discontinuation of study drug, or reintroduction of study drug (as applicable)
- Known association of the event with the study drug or with similar treatments
- Known association of the event with the disease under study
- Presence of risk factors in the patient or use of concomitant medications known to increase the occurrence of the event
- Presence of non-treatment-related factors that are known to be associated with the occurrence of the event.

**Table 4 Causal Attribution Guidance**

Is the adverse event suspected to be caused by the study drug on the basis of facts, evidence, science-based rationales, and clinical judgment?	
YES	There is a plausible temporal relationship between the onset of the adverse event and administration of the study drug, and the adverse event cannot be readily explained by the patient's clinical state, intercurrent illness, or concomitant therapies; and/or the adverse event follows a known pattern of response to the study drug; and/or the adverse event abates or resolves upon discontinuation of the study drug or dose reduction and, if applicable, reappears upon re-challenge.
NO	An adverse event will be considered related, unless it fulfills the criteria specified below. Evidence exists that the adverse event has an etiology other than the study drug (e.g., preexisting medical condition, underlying disease, intercurrent illness, or concomitant medication); and/or the adverse event has no plausible temporal relationship to administration of the study drug (e.g., cancer diagnosed 2 days after first dose of study drug).

For patients receiving combination therapy, causality will be assessed individually for each protocol-mandated therapy.

### **5.3.5 Procedures for Recording Adverse Events**

Investigators should use correct medical terminology/concepts when recording adverse events on the Adverse Event eCRF. Avoid colloquialisms and abbreviations.

Only one adverse event term should be recorded in the event field on the Adverse Event eCRF.

#### **5.3.5.1 Infusion-Related Reactions**

Adverse events that occur during or within 24 hours after study drug administration and are judged to be related to study drug infusion should be captured as a diagnosis (e.g., "infusion-related reaction" or "anaphylactic reaction") on the Adverse Event eCRF. If possible, avoid ambiguous terms such as "systemic reaction." Associated signs and symptoms should be recorded on the dedicated Infusion-Related Reaction eCRF.

Investigators should consider a local IRR for any symptoms affecting the skin and localized to only one place. Any other IRR should be considered as systemic.

If a patient experiences both a local and systemic reaction to the same dose of study drug, each reaction should be recorded separately on the Adverse Event eCRF, with signs and symptoms also recorded separately on the dedicated Infusion-Related Reaction eCRF.

#### **5.3.5.2 Diagnosis versus Signs and Symptoms**

A diagnosis (if known) should be recorded on the Adverse Event eCRF rather than individual signs and symptoms (e.g., record only liver failure or hepatitis rather than jaundice, asterixis, and elevated transaminases). However, if a constellation of signs

and/or symptoms cannot be medically characterized as a single diagnosis or syndrome at the time of reporting, each individual event should be recorded on the Adverse Event eCRF. If a diagnosis is subsequently established, all previously reported adverse events based on signs and symptoms should be nullified and replaced by one adverse event report based on the single diagnosis, with a starting date that corresponds to the starting date of the first symptom of the eventual diagnosis.

### **5.3.5.3 Adverse Events That Are Secondary to Other Events**

In general, adverse events that are secondary to other events (e.g., cascade events or clinical sequelae) should be identified by their primary cause, with the exception of severe or serious secondary events. A medically significant secondary adverse event that is separated in time from the initiating event should be recorded as an independent event on the Adverse Event eCRF. For example:

- If vomiting results in mild dehydration with no additional treatment in a healthy adult, only vomiting should be reported on the eCRF.
- If vomiting results in severe dehydration, both events should be reported separately on the eCRF.
- If a severe gastrointestinal hemorrhage leads to renal failure, both events should be reported separately on the eCRF.
- If dizziness leads to a fall and consequent fracture, all three events should be reported separately on the eCRF.
- If neutropenia is accompanied by an infection, both events should be reported separately on the eCRF.

All adverse events should be recorded separately on the Adverse Event eCRF if it is unclear as to whether the events are associated.

### **5.3.5.4 Persistent or Recurrent Adverse Events**

A persistent adverse event is one that extends continuously, without resolution, between patient evaluation time points. Such events should only be recorded once on the Adverse Event eCRF. The initial severity (intensity or grade) of the event will be recorded at the time the event is first reported. If a persistent adverse event becomes more severe, the most extreme severity should also be recorded on the Adverse Event eCRF. If the event becomes serious, it should be reported to the Sponsor immediately (i.e., no more than 24 hours after learning that the event became serious; see Section 5.4.2 for reporting instructions). The Adverse Event eCRF should be updated by changing the event from "non-serious" to "serious," providing the date that the event became serious, and completing all data fields related to serious adverse events.

A recurrent adverse event is one that resolves between patient evaluation time points and subsequently recurs. Each recurrence of an adverse event should be recorded as a separate event on the Adverse Event eCRF.

### **5.3.5.5 Abnormal Laboratory Values**

Not every laboratory abnormality qualifies as an adverse event. A laboratory test result must be reported as an adverse event if it meets any of the following criteria:

- Is accompanied by clinical symptoms
- Results in a change in study treatment (e.g., dosage modification, treatment interruption, or treatment discontinuation)
- Results in a medical intervention (e.g., potassium supplementation for hypokalemia) or a change in concomitant therapy
- Is clinically significant in the investigator's judgment

It is the investigator's responsibility to review all laboratory findings. Medical and scientific judgment should be exercised in deciding whether an isolated laboratory abnormality should be classified as an adverse event.

If a clinically significant laboratory abnormality is a sign of a disease or syndrome (e.g., alkaline phosphatase and bilirubin  $5 \times$  ULN associated with cholestasis), only the diagnosis (i.e., cholestasis) should be recorded on the Adverse Event eCRF.

If a clinically significant laboratory abnormality is not a sign of a disease or syndrome, the abnormality itself should be recorded on the Adverse Event eCRF, along with a descriptor indicating whether the test result is above or below the normal range (e.g., "elevated potassium," as opposed to "abnormal potassium"). If the laboratory abnormality can be characterized by a precise clinical term per standard definitions, the clinical term should be recorded as the adverse event. For example, an elevated serum potassium level of 7.0 mEq/L should be recorded as "hyperkalemia."

Observations of the same clinically significant laboratory abnormality from visit to visit should only be recorded once on the Adverse Event eCRF (see Section 5.3.5.4 for details on recording persistent adverse events).

### **5.3.5.6 Abnormal Vital Sign Values**

Not every vital sign abnormality qualifies as an adverse event. A vital sign result must be reported as an adverse event if it meets any of the following criteria:

- Is accompanied by clinical symptoms
- Results in a change in study treatment (e.g., dosage modification, treatment interruption, or treatment discontinuation)
- Results in a medical intervention or a change in concomitant therapy
- Is clinically significant in the investigator's judgment

It is the investigator's responsibility to review all vital sign findings. Medical and scientific judgment should be exercised in deciding whether an isolated vital sign abnormality should be classified as an adverse event.

If a clinically significant vital sign abnormality is a sign of a disease or syndrome (e.g., high blood pressure), only the diagnosis (i.e., hypertension) should be recorded on the Adverse Event eCRF.

Observations of the same clinically significant vital sign abnormality from visit to visit should only be recorded once on the Adverse Event eCRF (see Section 5.3.5.4 for details on recording persistent adverse events).

### 5.3.5.7 Abnormal Liver Function Tests

The finding of an elevated ALT or AST ( $>3 \times \text{ULN}$ ) in combination with either an elevated total bilirubin ( $>2 \times \text{ULN}$ ) or clinical jaundice in the absence of cholestasis or other causes of hyperbilirubinemia is considered to be an indicator of severe liver injury (as defined by Hy's law). Therefore, investigators must report as an adverse event the occurrence of either of the following:

- Treatment-emergent ALT or AST  $>3 \times \text{ULN}$  in combination with total bilirubin  $>2 \times \text{ULN}$
- Treatment-emergent ALT or AST  $>3 \times \text{ULN}$  in combination with clinical jaundice

The most appropriate diagnosis or (if a diagnosis cannot be established) the abnormal laboratory values should be recorded on the Adverse Event eCRF (see Section 5.3.5.2) and reported to the Sponsor immediately (i.e., no more than 24 hours after learning of the event), either as a serious adverse event or an adverse event of special interest (see Section 5.4.2).

### 5.3.5.8 Deaths

All deaths that occur during the protocol-specified adverse event reporting period (see Section 5.3.1), regardless of relationship to study drug, must be recorded on the Adverse Event eCRF and immediately reported to the Sponsor (see Section 5.4.2). This includes death attributed to progression of RRMS.

Death should be considered an outcome and not a distinct event. The event or condition that caused or contributed to the fatal outcome should be recorded as the single medical concept on the Adverse Event eCRF. Generally, only one such event should be reported. The term "**sudden death**" should be used only for the occurrence of an abrupt and unexpected death due to presumed cardiac causes in a patient with or without preexisting heart disease, within 1 hour after the onset of acute symptoms or, in the case of an unwitnessed death, within 24 hours after the patient was last seen alive and stable. If the cause of death is unknown and cannot be ascertained at the time of reporting, "**unexplained death**" should be recorded on the Adverse Event eCRF. If the cause of death later becomes available (e.g., after autopsy), "unexplained death" should be replaced by the established cause of death.

If the death is attributed to progression of RRMS, "RRMS progression" should be recorded on the Adverse Event eCRF.

### **5.3.5.9 Preexisting Medical Conditions**

A preexisting medical condition is one that is present at the screening visit for this study. Such conditions should be recorded on the General Medical History and Baseline Conditions eCRF.

A preexisting medical condition should be recorded as an adverse event only if the frequency, severity, or character of the condition worsens during the study. When recording such events on the Adverse Event eCRF, it is important to convey the concept that the preexisting condition has changed by including applicable descriptors (e.g., "more frequent headaches").

### **5.3.5.10 Lack of Efficacy or Worsening of Relapsing Remitting Multiple Sclerosis**

Events that are clearly consistent with the expected pattern of progression of the underlying disease, such as MS relapses or disability worsening should not be recorded as adverse events. These data will be captured as efficacy assessment data only. In most cases, the expected pattern of progression will be based on EDSS score. In rare cases, the determination of clinical progression will be based on symptomatic deterioration. However, every effort should be made to document progression through use of objective criteria. If there is any uncertainty as to whether an event is due to disease progression, it should be reported as an adverse event.

Occasional isolated symptoms that according to the investigator are caused by MS, but do not constitute a full MS relapse, should be reported as an AE, with the causality "Disease under study" (see Section 5.3.4).

### **5.3.5.11 Hospitalization or Prolonged Hospitalization**

Any adverse event that results in hospitalization (i.e., in-patient admission to a hospital) or prolonged hospitalization should be documented and reported as a serious adverse event (per the definition of serious adverse event in Section 5.2.2), except as outlined below.

The following hospitalization scenarios are not considered to be adverse events:

- Hospitalization for respite care
- Hospitalization for a preexisting condition, provided that all of the following criteria are met:
  - The hospitalization was planned prior to the study or was scheduled during the study when elective surgery became necessary because of the expected normal progression of the disease
  - The patient has not experienced an adverse event

The following hospitalization scenarios are not considered to be serious adverse events, but should be reported as adverse events instead:

- Hospitalization that was necessary because of patient requirement for outpatient care outside of normal outpatient clinic operating hours.
- Elective hospitalizations or surgical procedures that are a result of a patient's pre-existing condition(s) that have not worsened since receiving trial medication. Examples may include, but are not limited to, cholecystectomy for gallstones, and diagnostic testing. Such events should still be recorded as medical procedures in the "Surgeries and therapies" eCRF.
- Hospitalization to receive trial medication such as infusions of ocrelizumab unless this is prolonged (more than 24 hours).
- Hospitalization following an MS relapse as long as the reason for hospitalization is to receive standard treatment with i.v. methylprednisolone.

For a list of serious ADRs that are considered expected, kindly refer to the current IB.

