### **4.3.2 Dosage, Administration, and Compliance**

#### **4.3.2.1 Ocrelizumab**

The first dose of ocrelizumab will be administered as two 300-mg infusions (600 mg total) in 250 mL 0.9% sodium chloride each separated by 14 days (i.e., Days 1 and 15), followed by one 600-mg infusion in 500 mL 0.9% sodium chloride every subsequent dose (i.e., every 24 weeks) for a maximum of 4 doses.

It is anticipated that the patient will need to stay at the hospital or clinic for a full day for the infusion visits. Ocrelizumab infusions should be initiated and supervised by an experienced professional with access to appropriate medical support to manage severe reactions such as serious IRRs. Each ocrelizumab infusion should be given as a slow IV infusion over approximately 150 minutes (2.5 hours) for the 300 mg dose and approximately 215 minutes (3.6 hours) for the 600 mg dose. To reduce potential IRRs, all patients will receive prophylactic treatment with 100 mg of methylprednisolone, or equivalent, administered by slow IV infusion, to be completed approximately 30 minutes before the start of each ocrelizumab infusion, and an antihistaminic drug (e.g., diphenhydramine) approximately 30–60 minutes before each infusion of ocrelizumab. Additional premedication is recommended, see [Section 4.3.3](#).

Hypotension, as a symptom of IRR, may occur during ocrelizumab IV infusions. Therefore, withholding antihypertensive treatments should be considered for 12 hours prior to and throughout each ocrelizumab infusion.

Ocrelizumab must not be administered as an IV push or bolus. Well-adjusted infusion pumps should be used to control the infusion rate, and ocrelizumab should be infused through a dedicated line. It is important not to use evacuated glass containers, which require vented administration sets, to prepare the infusion because this causes foaming as air bubbles pass through the solution.

The patient will need to remain at the clinic at every visit for at least 1 hour after the completion of the infusion for observation. After completion of the infusion, the IV cannula should remain in situ for at least 1 hour to allow for administration of drugs

intravenously, if necessary, in the event of a delayed reaction. If no adverse events occur during this period of time, the IV cannula may be removed, and the patient may be discharged.

See the Ocrelizumab IB and Drug Preparation Guidelines for detailed instructions on drug preparation, storage, and administration.

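### Protocol 5.3.5.11 directs sites to report two event-free scenarios as adverse events (admission only for the infusion, and elective surgery for an unchanged condition), against the protocol's own definitions

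*Protocol*

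**What the plan says.** Section 5.3.5.11 opens by making any adverse event that leads to in-patient admission a serious adverse event, subject to two lists of exceptions.

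- **First list (not adverse events).** It covers respite care, and admission for a pre-existing condition if two conditions both hold: "The hospitalization was planned prior to the study or was scheduled during the study when elective surgery became necessary" through the expected course of the disease, and the patient has had no adverse event.
- **Second list.** Its heading is "The following hospitalization scenarios are not considered to be serious adverse events, but should be reported as adverse events instead". Two of its four items matter most here: "Elective hospitalizations or surgical procedures that are a result of a patient's pre-existing condition(s) that have not worsened since receiving trial medication", with cholecystectomy for gallstones as an example, and "Hospitalization to receive trial medication such as infusions of ocrelizumab unless this is prolonged (more than 24 hours". The other two are admission because outpatient care was needed outside clinic hours, and admission after an MS relapse for standard steroid treatment.

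Elsewhere, Section 5.2.1 says that "an adverse event is any untoward medical occurrence in a clinical investigation subject" given a pharmaceutical product. Section 5.3.5.9 says that a pre-existing condition "should be recorded as an adverse event only if the frequency, severity, or character of the condition worsens" during the study.

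On the setting, Section 5.1 allows infusion in a hospital, a clinic or a doctor's office, and Section 4.3.2.1 expects that "the patient will need to stay at the hospital or clinic for a full day for the infusion visits".

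SAP 4.6.2 counts all TEAEs by event and by patient, overall, by epoch, and by system organ class and preferred term. It has no rule for records that consist only of an admission or a procedure.

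**The concern.** The rate and nature of adverse events is the first safety endpoint (Protocol 2.2). The trial has one arm, so a reporting artefact is not offset by the same artefact in a control group. If sites follow the second list as printed, some TEAE records will describe logistics or a planned operation and nothing that happened to the patient's health. Sites that notice the conflict may resolve it in different ways, so the same admission could be recorded at one site and not at another. The tables as specified would not show how many records arose this way.

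**Working it through.** The plan states no figure on this point, so the main check is to set the rules side by side.

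**1. Admission only to receive ocrelizumab, 24 hours or less.** Suppose the infusion is given and nothing else happens. Section 5.2.1 names unfavourable signs or symptoms, new or exacerbated disease, recurrence of an intermittent condition, relevant deterioration in a test, and adverse events related to a protocol-mandated intervention. None fits an uneventful stay; the last still presupposes an adverse event. The second list nevertheless says to report it.

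**2. Elective admission or surgery for a pre-existing condition.** No adverse event has occurred and the condition is unchanged.

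| Case | First list | Second list | 5.3.5.9 |
|---|---|---|---|
| Planned before the study | Not an adverse event | Report as adverse event | Nothing to record |
| Scheduled during the study, no disease progression | Conditions not met | Report as adverse event | Nothing to record |

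In the top row, Section 5.3.5.11 gives two answers for the same operation. In the bottom row the two lists do not collide, but the second list still conflicts with 5.3.5.9. That section is about recording the condition, so the conflict is by implication: if nothing has worsened, there is no event for the operation to be part of.

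**3. A related conflict in the same list.** Admission after a relapse for standard treatment is to be reported as an adverse event. Section 5.3.5.10 says relapses consistent with the expected course of the disease are not recorded as adverse events and are captured as efficacy data only.

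**4. Which outputs are reached.** The overall TEAE counts and patient incidence in SAP 4.6.2 take in every reported record. The related-event lines move only if the investigator answers yes on causality. The SAP's list of rates per 100 patient-years covers fatal events, infusion-related reactions, infections, discontinuations, dose modifications, related events and Grade 3 or higher. It has no line for all adverse events.

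**5. Scale, as illustration only.** Inputs: 750 patients (Protocol 3.1.5); five infusions each, on Days 1 and 15 and at Weeks 24, 48 and 72 (Protocol Table 1); and 83.3% of patients with any adverse event in the pooled Phase III relapsing MS studies (Protocol 1.2). The share *s* given as in-patient admissions is assumed; the documents give none.

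- Planned infusions, at most: 750 × 5 = 3750.
- Added records: 3750 × *s*.
- Any-event incidence, if a share *s* of patients has at least one such admission, independently of other events: 83.3% + 16.7% × *s*.

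| *s* | Added records | Any-event incidence |
|---|---|---|
| 0% | 0 | 83.3% |
| 1% | 38 | 83.5% |
| 5% | 188 | 84.1% |
| 10% | 375 | 85.0% |
| 25% | 938 | 87.5% |
| 100% | 3750 | 100% |

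The two result columns use the same *s* only if admitted patients are admitted for every infusion. Elective operations are not included; nothing in the documents allows a count.

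**The case against.** The strongest reply is the opening sentence of Section 5.3.5.11. It concerns adverse events that result in hospitalization, and both lists are exceptions to it. On that reading the second list only lowers seriousness when an adverse event already exists, and an uneventful infusion admission never enters it. This is a possible reading and agrees with Section 5.2.1. But the heading of the list refers to scenarios, the two items describe no underlying event, and nothing states the restriction. Nor does this reading remove the overlap between the lists for surgery planned before the study.

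Other parts of the reply stand:

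- Hospitalization means in-patient admission. Section 4.3.2.1 describes a day visit: an infusion of about 2.5 or 3.6 hours, at least one hour of observation, then discharge. No document says that any site admits patients for infusion.
- The first list is conditional, so not every elective operation falls under both lists.
- Any error is over-reporting of non-serious records. The rule does not in itself create serious events, deaths, infections or infusion-related reactions. Tabulation by preferred term and the full listing would let a careful reader see admission or procedure terms.
- Taking reported records out of the main tables of an open-label trial would be a debatable exclusion.

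**Conclusion.** Section 5.3.5.11 is wrong as written. Two items on its second list conflict with Section 5.2.1. One of them also conflicts with Section 5.3.5.9 and, for surgery planned before the study with no adverse event, with the first list of the same section. Read literally, the rule puts non-events into the overall TEAE counts and incidence. How many is unknown: none if all infusions are day cases and no such operations occur.

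A reader might infer more, and the documents do not support it:

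- **That every dose creates an adverse event, or that the trial's adverse event rates are driven by local admission practice.** This needs in-patient infusion to be common, and no share is given.
- **That the SAP's rates per 100 patient-years are inflated.** There is no all-event line, and the related-event line depends on causality calls that cannot be predicted from the text. Protocol 6.5.2 mentions rates in general, but SAP Section 4 says its analyses supersede the protocol's.
- **That comparisons by last prior treatment are distorted.** Nothing links admission practice to prior treatment.

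**What to change.** Reconcile Sections 5.2.1, 5.3.5.9 and 5.3.5.11 in one of two ways:

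- move the infusion-admission item (24 hours or less) and the unchanged-condition item to the list of scenarios that are not adverse events; or
- state that the second list applies only when an adverse event has occurred.

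Either way, keep procedures on the Surgeries and therapies eCRF page and still report any event that happens during the stay. Reconcile the relapse-admission item with Section 5.3.5.10 in the same amendment.

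For data already collected, leave the reported records in the main TEAE tables. In the SAP, define before database lock a rule that flags records consisting only of an admission or a procedure, list them, and add one supplementary TEAE count and incidence without them.

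The cost is a wording change, a memo to sites and one review of adverse event terms before lock. No safety information is lost.
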